At the conclusion of the study, we will censor any subject who reports using systemic antibiotics during the 8-week study period. This will prevent antibiotic use from confounding our microbiota results. As this study is a randomized controlled study, the analysis for the primary outcome will consist of testing for differences in changes in bacterial biomass between the two patient groups using a 2 sample *t*-test with equal variances between groups. While it is widely recognized that the *t*-test is robust with regard to departures from the normality assumption, if the data appear very non-normal (as observed in a *qq*-plot) even after standard transformations are considered (such as the Box-Cox transformation) then Wilcoxon's test will be used. Similarly, if the variance is markedly different between the groups then Welch's 2 sample *t*-test will be used. While randomization should ensure that the groups are balanced on important potential confounders (such as age) all such factors will be examined to check that there are not significant differences between the groups. If there are differences then linear models will be fit to account for these potential confounders (again, standard transformations will be considered to improve model fit and diagnostics will be performed to assess model assumptions).

The analysis for secondary endpoints necessarily takes a different strategy as that investigates the relationship among variables that are not subject to direct randomization. Hence the analysis will consider regression models that investigate how changes in health status (as measured by changes in the SGRQ) depend on microbial diversity and inflammatory markers. Model selection will be guided by scientific plausibility, model diagnostics and measures of model quality (such as AIC).

Sample Size and Power Calculation

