We can use the preliminary data on microbial diversity among COPD patients to estimate the power of the study. For concreteness we will assess the power for detecting a difference in the Simpson (1-D) diversity measure (the correlation between this measure and Shannon's measure was 0.96 in our preliminary data). The standard deviation in this measure among moderately affected COPD patients is 0.280 and is 0.298 among the severely affected COPD patients, and as there is no significant difference between the variances ($p=0.80$ by Bartlett's test) we combine the data from both groups and obtain an estimate of 0.281 for the standard deviation. To obtain an estimate of the magnitude of differences that are reasonable to expect from a drug that decreases the diversity of the lung flora, we fit a linear regression model with diversity as the outcome and age as the predictor variable (the ages range from 55 to 78 among these subjects). Age has a significant positive impact on diversity ($p=0.047$)

with an estimated slope of 0.017, so that over the course of 20 years the model predicts that there will be a change of 0.34 in diversity. Hence we investigated the power for values of the difference attributable to the effect of chlorhexidine from 0.22 to 0.32 and present the results in Table 1 (these results are from a 2 sample *t*-test with equal variance using the estimated standard deviation from the previous study and 20 subjects per group). These results indicate that the study should have acceptable power if chlorhexidine has an impact on the diversity of the lung microbiota that is comparable to what is observed due to the effect of aging. We will increase the sample size to 25 per group since we anticipate censoring at least 20% of the subjects because of antibiotic use during the study. This population has a demonstrated exacerbation rate of approximately 20% and exacerbations are often treated with antibiotics.

Effect size	0.22	0.24	0.26	0.28	0.30	0.32
Power	0.67	0.75	0.81	0.87	0.91	0.94

Table 1: The power of the study to detect a difference between the treatment groups as it depends on the magnitude of the difference in diversity between the 2 groups.

Quality Control

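### The primary biomass test is chosen among equal-variance t, Welch and Wilcoxon after looking at the outcome data, with no stated trigger or priority, so a 5% level is not guaranteed; naming one test removes this at almost no cost

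*Combined protocol and SAP*

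**What the plan says.** The Data Analysis Plan describes the primary analysis as "testing for differences in changes in bacterial biomass between the two patient groups using a 2 sample" t-test that assumes equal variances. Two departures follow.

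- **To Wilcoxon:** the trigger is a visual judgement that the qq-plot is far from normal, and it applies only once other scales have been tried: "even after standard transformations are considered (such as the Box-Cox transformation) then Wilcoxon's test will be used".
- **To Welch:** "if the variance is markedly different between the groups then Welch's 2 sample" t-test is substituted.

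A third data-driven step concerns baseline imbalance: "If there are differences then linear models will be fit to account for these potential confounders".

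The plan does not say how large a departure counts, which switch takes precedence if both apply, who decides, whether that person is masked to arm, or whether the tests not chosen are reported. It states neither a significance level nor sidedness.

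**The concern.** A test selected from the data it will be applied to does not automatically keep the error rate of any of its components. Here the variance check uses the outcome by arm, and the cut-off is left to judgement.

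The trial has some exposure. Antibiotic users are removed after randomisation, and Sample Size and Power Calculation expects to lose at least 20% this way, so the analysed arms may be unequal despite 1:1 allocation. No SD for biomass change is given. The Bartlett comparison in that section concerns diversity across two COPD severity groups, so it does not support equal variance of biomass change between treatment arms.

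At stake are the error rate of the primary p-value and what it refers to. Wilcoxon does not in general estimate a difference in mean change, so the effect carried into the larger trial the protocol foresees could depend on which branch was taken.

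**Working it through.** **The plan's own figure.** Inputs from Sample Size and Power Calculation: SD 0.281, 20 per group, equal-variance t-test, differences 0.22 to 0.32 in Simpson diversity. The noncentrality is δ / (σ√(2/n)) on 38 df. For δ = 0.26 this is 0.26 / (0.281 × √0.1) = 2.93, and power at two-sided 0.05 is 0.814 (Table 1: 0.81). The full row is 0.675, 0.749, 0.814, 0.867, 0.908, 0.939 against the printed 0.67, 0.75, 0.81, 0.87, 0.91, 0.94. One-sided 0.05 would give 0.78 to 0.97. The level is therefore inferred to be two-sided 5%. The inflation also checks: 20 / (1 − 0.20) = 25. All this concerns diversity; the documents give no type I error figure for biomass to reproduce.

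**Type I error by simulation.** At least 40,000 runs per case, no mean difference, two-sided 5%. Monte Carlo error at 40,000 runs is about √(0.05 × 0.95 / 40,000) = 0.1 point. Arm splits, SD ratios and all cut-offs are assumptions, because the documents give none.

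- *20/20, equal SDs, normal:* equal-variance t 5.0%, Welch 5.0%, Wilcoxon 4.9%. A t/Welch switch gives 5.1%. A three-way rule (Wilcoxon if the qq-plot correlation falls below its 5% normal cut-off, otherwise Welch if the variance ratio exceeds 2, otherwise t) gives 5.2%.
- *20/20, SD ratio 2, normal:* equal-variance t 5.2%; t/Welch switch 5.0% to 5.1%. Adding the assumed Wilcoxon branch raises the rule to 6.2% to 6.3%.
- *17/23, SD ratio 2, smaller arm more variable, normal:* equal-variance t about 7.5%, Wilcoxon 6.8%, Welch 5.0%. The t/Welch switch depends on its cut-off for the variance ratio: 5.0% at 1.5, about 5.1% at 2, 5.7% at 3, and 6.2% to 6.4% at 4 across repeated runs. A cut-off of 2 fires in over 90% of trials; a cut-off of 4 fires in about 49%.
- *17/23, larger arm more variable, normal:* equal-variance t 3.5%, which is conservative.
- *20/20, exponential shape, equal means, SD ratio 2:* equal-variance t 6.3%, Welch 6.2%, Wilcoxon 19.0%, three-way rule 19.2%. The Wilcoxon figure is not a miscalculation. A mean-zero exponential with SD s has median s(ln 2 − 1) = −0.307s, so the arm medians are −0.307 and −0.614 while the means are equal. The test responds to a real difference in distribution that is not a difference in mean change.

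**How likely is an unequal split?** With 25 per arm and independent 20% censoring, a gap of six or more (17/23 or wider) has probability about 5%. The smaller arm is the more variable one in half of those, about 2.5%. A gap of ten (15/25) has probability under 0.1%.

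**Does the choice change the conclusion?** At 20/20 with equal SDs and a true effect of 0.6 SD, the three tests do not all agree at 5% in about 7% of trials. At 0.26 / 0.281 = 0.925 SD the figure is 5%. Almost all of this involves Wilcoxon: t and Welch alone differ in at most 0.1% of such trials.

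**The case against.** The best defence is that the plan names a default and two fallbacks, each triggered by a distributional diagnostic and not by a p-value, and that in the most likely setting this costs almost nothing. That stands. A reader might infer that the primary test fails to hold 5%; the documents do not support so flat a statement. If the rinse has no effect, randomisation gives both arms the same distribution of change, which is the benign case unless the censoring itself distorts it. Equal means with unequal spread is a narrower null that the documents do not suggest.

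Direction is also open. If chlorhexidine prevented exacerbations, the placebo arm would lose more patients; if it also widened the spread of change among treated patients, the larger arm would be the more variable one and the t-test conservative.

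Three further readings go too far.

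- The highest error rate comes from reporting whichever of the three tests is significant (5.9% to 6.1% at 20/20 with equal SDs). The plan does not allow this, so it is a worst case only.
- The rates above 6% for a t/Welch switch need a cut-off near 4, which is nowhere in the documents.
- Box-Cox is undefined for zero or negative change scores, but the plan does not say it is applied to the change; copy numbers could be transformed before differencing.

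The Welch switch is the least consequential step, and Welch improves error control when variances differ. The objection does not supply the missing trigger or priority, and it does not answer the change of hypothesis under Wilcoxon.

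**Conclusion.** The point holds in a limited form. The selection rule is incompletely specified and uses outcome data, so a 5% level is not guaranteed. The excess is 0.1 to 0.2 point in the benign case and becomes material in two situations: unequal arms with more spread in the smaller one, where the error rate depends on an unstated cut-off, and the Wilcoxon branch under skewness with unequal spread. The first needs a split that random 20% censoring produces in about one trial in twenty; censoring that differs by arm could make it more common, by an amount the documents do not let one estimate. The size of the second depends on the assumed shape.

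All of this rests on an inferred two-sided 5% level and on assumed splits, SD ratios and triggers. For a self-described pilot it is a cheap improvement and not a flaw that undermines the trial.

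**What to change.** In the Data Analysis Plan, replace the conditional sentences on test choice with one rule:

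- The primary comparison is Welch's two-sample t-test, or a linear model with heteroskedasticity-robust standard errors if an adjusted analysis is chosen in advance, at two-sided 5%.
- It is applied once, on a single scale fixed before unmasking, for example change in log 16S copies with the transformation applied before differencing.
- The difference is reported with its 95% confidence interval.
- Inspection of the variances no longer changes the test.
- Wilcoxon with the Hodges-Lehmann shift is a sensitivity analysis and does not replace the primary result.

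Welch fixed in advance held 4.8% to 5.3% across the normal-data cases. It is not a full cure for skewness combined with unequal spread (6.2% at 20/20 in the exponential case), which is a further reason to fix a suitable scale.

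The cost is a few sentences. With equal variances and a 0.9 SD effect, simulated power is 79.2% against 79.3% for the equal-variance test at 20/20, and 78.0% against 78.3% at 17/23.

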Date: 3/31/2014
NCT: NCT02252588

STUDY PROTOCOL

Title: The Effect of Chlorhexidine on the Oral and Lung Microbiota in Chronic Obstructive Pulmonary Disease

Investigators:

[name] Principal Investigator
[name]
[name]
[name]
[name]

A. Specific Aims

Aim 1. Determine the effect of twice-daily chlorhexidine oral rinse on oral and lung microbiota biomass in subjects with chronic obstructive pulmonary disease (COPD) with chronic bronchitis. Our primary outcome will be to compare the microbiota biomass (number of bacteria as measured by 16S rRNA copy number) of *induced sputum* and the *oral cavity* before and after 8 weeks of twice-daily chlorhexidine oral rinse (n=25) compared to controls (n=25) using qPCR and next-generation sequencing of the bacterial 16S rRNA gene comparing total bacterial biomass.

Our *hypothesis* is that 8 weeks of chlorhexidine oral rinse will decrease microbiota biomass compared to baseline and those on placebo. Furthermore, we hypothesize that chlorhexidine treatment will: i) decrease lung and oral microbiota diversity; ii) alter microbiota taxonomic composition in the lung and oral cavity; iii) decrease systemic inflammation as measured by blood high sensitivity C-reactive protein (hsCRP), fibrinogen and leukocyte count; and iv) demonstrate a trend towards improvement in respiratory health status as measured by the Breathlessness, Cough, and Sputum Scale (BCSS)[1, 2] and St. George's Respiratory Questionnaire (SGRQ).

Subaim 1: Determine if chlorhexidine alters the lung and oral rinse microbiota diversity and taxonomic composition. Our *hypothesis* is that chlorhexidine oral rinse will decrease the diversity (Shannon and inverse Simpson diversity indices) and taxonomic composition of both oral and lung microbiota compared to those on placebo as determined by next-generation sequencing of the bacterial 16S rRNA gene.

Subaim 2: Determine the impact of chlorhexidine on systemic inflammation. Our *hypothesis* is that the decrease in lung microbiota biomass is associated with a decrease in systemic inflammation as measured by blood hsCRP, fibrinogen, and leukocyte count.

Subaim 3: Determine if respiratory symptoms associate with the lung microbiota biomass. Our *hypothesis* is that chlorhexidine will demonstrate improved respiratory health status as measured by the BCSS and SGRQ.

B. Background and Significance

COPD and Chronic Obstructive Bronchitis are major health concerns

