The potential benefit of oral decontamination in the treatment of COPD remains unknown. We have compelling evidence that the COPD lung microbiota is more diverse than healthy lungs and is a reflection of the oral microbiota, presumably due to repeated aspiration and decreased clearance. In addition, it is well established that bacteria are a major cause of COPD exacerbations. Therefore, it seems plausible that the oral microbiota is a major contributor in COPD and especially in COPD exacerbations. Chlorhexidine is a broad-spectrum antiseptic that is safe, well-tolerated and shown to decrease respiratory infection associated with oral intubation. We hypothesize that twice daily oral rinses with chlorhexidine will result in a decrease in the lung microbiota biomass. If proven correct, this would be the basis for a large interventional trial to determine if oral decontamination with chlorhexidine will decrease COPD exacerbations.

C. Work Proposed

Overview

The *primary outcome* of this pilot study is to determine if twice-daily chlorhexidine oral rinse decreases the microbiota biomass, as measured by 16S rRNA copy number, in the COPD lung and oral cavity as measured in induced sputum and oral wash. Our *secondary outcome* are to determine if chlorhexidine oral rinse: i) decreases lung and oral microbiota diversity; ii) alters taxonomic composition of the lung and oral cavity microbiota; iii) decreases systemic inflammation as measured by blood hsCRP, fibrinogen and leukocyte count; and iv) changes in respiratory health status as measured by the BCSS and SGRQ. If our hypotheses are supported, this study will form the basis of an interventional trial to determine if altering the oral microbiota with chlorhexidine can prevent COPD exacerbations.

Study Design Overview

This study will determine if the microbiota of the oral cavity and induced sputum is altered by twice-daily chlorhexidine rinse. At *baseline*, the following studies will be done:

1. Spirometry to determine study eligibility and to guide sputum induction protocol.
2. Oral rinse and induced sputum for microbiota analysis. An oral rinse of 15 ml sterile water and induced sputum will be obtained at baseline for microbiota analysis.
3. Inflammatory markers (blood hsCRP, fibrinogen, and leukocyte count).
4. Breathlessness, Cough and Sputum Scale (BCSS). This 3-item self-completed questionnaire focuses on common COPD symptoms.

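### The Data Analysis Plan states no between-arm comparison for any of 9 secondary efficacy measures, on a rationale that fits only the association questions

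*Combined protocol and SAP*

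**What the plan says.** For the primary outcome, the Data Analysis Plan relies on randomisation and specifies "testing for differences in changes in bacterial biomass between the two patient groups" by a two-sample t-test, with Wilcoxon's or Welch's test as fallback.

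For secondary endpoints it says a different strategy is necessary, because the analysis "investigates the relationship among variables that are not subject to direct randomization". The only analysis then named is "regression models that investigate how changes in health status (as measured by changes in the SGRQ) depend on microbial diversity and inflammatory markers". Model choice is left to plausibility, diagnostics and measures such as AIC.

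The secondary questions are worded elsewhere:

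- Section C, Overview: the secondary outcomes are to "determine if chlorhexidine oral rinse: i) decreases lung and oral microbiota diversity; ii) alters taxonomic composition of the lung and oral cavity microbiota". The same sentence goes on to systemic inflammation (hsCRP, fibrinogen, leukocyte count) and to health status (BCSS, SGRQ).
- Section A, Subaim 1: chlorhexidine will "decrease the diversity (Shannon and inverse Simpson diversity indices) and taxonomic composition of both oral and lung microbiota compared to those on placebo".
- Section A, Subaim 2: the title asks about the impact of chlorhexidine on inflammation, but the hypothesis is that "the decrease in lung microbiota biomass is associated with a decrease in systemic inflammation".
- Section A, Subaim 3: the title is "Determine if respiratory symptoms associate with the lung microbiota biomass", but the hypothesis is that "chlorhexidine will demonstrate improved respiratory health status as measured by the BCSS and SGRQ".

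The Sample Size and Power Calculation section bases Table 1 on an equal-variance two-sample t-test of Simpson (1-D) diversity between treatment groups, with 20 subjects per group.

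**The concern.** In a trial, treatment is randomised and outcomes are not. Diversity, hsCRP or SGRQ can be compared between arms with the same justification as biomass. The stated reason holds when one measured variable is related to another, as in the Subaim 2 hypothesis and the Subaim 3 title. It does not hold when the question is what chlorhexidine does compared with placebo, and most of the secondary questions are of that kind.

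The rule is therefore more than an omitted detail: it directs the secondary analysis away from the trial's own questions. If it is followed as written, arm comparisons for these outcomes would have to be added later, with the index, the contrast and the covariates still open once data are in hand. Section C presents the study as the basis for a larger trial, and estimates by randomised arm are what that trial would need.

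**Working it through.** **1. The plan's own figure.** Inputs from the sample size section: SD 0.281, n = 20 per group, differences 0.22 to 0.32. Alpha and sidedness are not stated; two-sided 0.05 is assumed. The noncentrality is d / (SD × √(2/n)), with 38 degrees of freedom. For d = 0.26 this is 0.26 / (0.281 × √0.1) = 0.26 / 0.0889 = 2.93.

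| Difference | 0.22 | 0.24 | 0.26 | 0.28 | 0.30 | 0.32 |
|---|---|---|---|---|---|---|
| Recomputed power | 0.675 | 0.749 | 0.814 | 0.867 | 0.908 | 0.939 |
| Table 1 | 0.67 | 0.75 | 0.81 | 0.87 | 0.91 | 0.94 |

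Table 1 is reproduced, and so is the step to 25 per group: 20 / (1 − 0.20) = 25. A between-arm diversity test was therefore in view when the trial was sized.

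**2. The count.** The measures come from the Secondary Outcomes list; adverse effects are a safety item and are left out.

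| Measure | Number | Posed as a chlorhexidine effect in | Role in the Data Analysis Plan | Arm comparison stated there |
|---|---|---|---|---|
| Diversity (sputum, oral) | 2 | Overview; Subaim 1 | Predictor of SGRQ change | No |
| Taxonomy (sputum, oral) | 2 | Overview; Subaim 1 | None | No |
| hsCRP, fibrinogen, leukocytes | 3 | Overview; Subaim 2 title | Predictors of SGRQ change | No |
| BCSS | 1 | Overview; Subaim 3 hypothesis | None | No |
| SGRQ | 1 | Overview; Subaim 3 hypothesis | Regression outcome | No |

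2 + 2 + 3 + 1 + 1 = 9 measures, with 0 arm comparisons. Counting Shannon and inverse Simpson separately at each site adds 2, giving 11, still with 0.

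**3. What the named regression can answer.** It relates SGRQ change to diversity and inflammatory markers. With no treatment term stated, it estimates no effect of chlorhexidine. Adding an arm term beside predictors measured after randomisation would not give the total treatment effect either, because it would hold fixed variables that the rinse is meant to change. With no biomass term stated, it does not address the biomass associations in Subaims 2 and 3, which are the questions the rationale does fit.

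**4. What the implied diversity test leaves open.** The sample size section does not say whether the week-8 value or the change is compared. Section A names Shannon and inverse Simpson; the sample size section uses Simpson 1-D as a concrete example.

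**5. Two further gaps.** BCSS is a questionnaire completed at visits in the Study Design Overview and a daily diary in its own section. The Data Analysis Plan removes subjects who used systemic antibiotics, for a reason that concerns the microbiota results only. It does not say whether the blood markers, BCSS and SGRQ are analysed in that reduced set.

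**The case against.** This is one combined document and a self-described pilot. A colleague could fairly say that a diversity comparison between arms is visible in the sample size section, that the regressions are deliberately open-ended, and that Section A expects only a trend in health status. Much of this stands, and it rules out three stronger readings.

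- A reader might infer that the plan provides no randomised estimate at all, diversity included. The documents do not support that: the power section names a two-sample t-test between arms. It appears there as a power assumption, however, and the Data Analysis Plan, which calls a different strategy necessary, does not take it up. For the other outcomes no such test appears anywhere.
- A reader might infer that treatment and biomass are excluded from the regressions. The text shows only that neither is stated.
- A reader might infer a definite inflation of the false-positive rate. That would need the correlation between baseline and week 8, which the documents do not give, and an analyst who reports the best of several tests, which they do not describe.

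The index question is also small. The power section reports a correlation of 0.96 between Simpson 1-D and Shannon. Inverse Simpson is a monotone transform of 1-D, so a rank test on single-time values would give the same result.

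Pilot status limits the stakes, but it does not make the rationale fit treatment-effect questions.

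**Conclusion.** The concern holds in a limited form. The Data Analysis Plan applies to secondary endpoints as a class a reason that is valid only for associations. It states an arm comparison for 0 of 9 secondary efficacy measures that the protocol poses as effects of chlorhexidine (0 of 11 if both diversity indices are counted). For diversity alone, a comparison is implied by the power calculation but not planned.

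The primary analysis, the sample size and Table 1 are unaffected. The conclusion rests on reading the text as written; the only numerical assumption is two-sided 0.05 in reproducing Table 1. It should be corrected before analysis, but it does not threaten the main result.

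**What to change.** 1. Confine the rationale and the regressions to exploratory association analyses. Fix the predictors in advance and include biomass, since Subaims 2 and 3 ask about it.
2. State one between-arm comparison for each secondary outcome. For continuous outcomes, use a linear model of the week-8 value on arm, adjusted for the baseline value and the inhaled-corticosteroid stratum used in randomisation. This differs from the primary test and should be described as such. At minimum, extend the primary's two-sample test on change.
3. Name one diversity index as the main one.
4. Compare taxonomic composition between arms by a prespecified method; a permutation test is one option.
5. State which BCSS score is analysed.
6. State whether the antibiotic censoring applies to the blood markers, BCSS and SGRQ. Analysing these in all randomised subjects keeps the randomised comparison intact.
7. Report estimates with confidence intervals and label them supportive.

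No new data, visits or subjects are needed. The cost is analysis-plan wording, decisions on the BCSS score and the analysis set, a little more analysis work, and more secondary tests that must be read cautiously.
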